6.1 OVERVIEW OF STUDY DESIGN

This study is a fixed-dose, randomized, two-arm Phase 3 trial to assess the efficacy and safety of ublituximab in combination with ibrutinib compared to ibrutinib alone in patients with CLL who have received at least one prior standard treatment regimen and who have at least one high-risk cytogenetic abnormality (17p deletion, 11q deletion, and/or P53 gene mutation).

Following screening, patients meeting the inclusion/exclusion criteria will be randomized in a 1:1 ratio, to either:

[figure not shown]
- Arm A: Ublituximab + ibrutinib; or
- Arm B: Ibrutinib

Randomized patients will be stratified according to prior lines of therapy (1 prior vs 2 or more prior lines of therapy).

All study patients will be evaluated for response after cycles 2, 4, and 6, then every 3 cycles thereafter if patient is on active treatment, or approximately every 3 months thereafter if patient is in follow up. The best clinical response as well as disease progression will be determined by an Independent Review Committee (IRC).

Patients will continue treatment until the occurrence of definitive disease progression, unacceptable toxicity, or withdrawal from the study due to investigator decision or other reasons. Patients who discontinue study treatment for reasons other than disease progression will continue to be followed for progression and/or survival approximately every 3 months.

Upon first assessment scan, or confirmation scan (if necessary), of the last randomized patient, and site submission of all required efficacy and safety data, the independent DSMB will review the primary and secondary efficacy analyses, and safety data.

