6.4 DISCONTINUATION FROM STUDY TREATMENT

Patients will be discontinued from study treatment for any of the following reasons:

- Disease progression
- Intolerable toxicity related to study drug
- Patient requests to withdraw consent or discontinue treatment
- Pregnancy
- Inability of the patient to comply with study requirements
- Conditions requiring therapeutic intervention not permitted by the protocol
- Non-compliance/lost to follow-up
- Investigator discretion
- Discontinuation of the study by the Sponsor

Patients who discontinue from study treatment (for reasons other than progressive disease) will continue to be followed for progression. **Every attempt to continue to follow the patient for progression should be made.**

After withdrawal from protocol treatment, patients should be followed for AEs for 30 calendar days after their last dose of either study drug. All new AEs occurring during this period must be reported and followed until resolution, unless, in the opinion of the investigator, these values are not likely to improve because of the underlying disease. In this case the investigators must record his or her reasoning for this decision in the patient's medical records and as a comment on the electronic Case Report Form (eCRF).

All patients who have CTCAE Grade 3 or 4 laboratory abnormalities at the time of withdrawal should be followed until the laboratory values have returned to Grade 1 or 2, unless in the opinion of the investigator, it is not likely that these values are to improve because of the underlying disease. In this

UTX-IB-301

case, the investigator must record his or her reasoning for making this decision in the patient's medical records and as a comment on the eCRF.

UTX-IB-301

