10 MEASUREMENT OF EFFECT

During the study period, all patients will be evaluated for response by CT and/or MRI after the completion of cycles 2, 4, and 6 then after the completion of every 3 cycles thereafter while under protocol treatment. If a patient is off study in follow up, assess for response every 3 months. All efficacy assessments have a +/- 7 day window. The determination of response and progression will be based on IWCLL criteria (Hallek M, 2008). Radiographic and clinical tumor assessments will be subject to independent confirmation by the Independent Review Committee (IRC) which will be blinded to treatment assignment. The findings of the IRC will be considered primary for analyses of ORR, PFS, and other tumor control endpoints.

CT scan is the preferred method of tumor assessment but MRI may be used at the investigator's discretion. The same method of assessment and the same technique should be used to characterize each identified and reported lesion at baseline and throughout the study. Please see study manual for detailed instructions for tumor assessment, and submission of scans for independent review.

All baseline assessments to characterize disease will be performed within 30 days of Cycle 1 Day 1, prior to initiation of therapy.

Patients will remain on study treatment until the occurrence of definitive disease progression, unacceptable toxicity, or withdrawal from the study due to investigator decision or other reasons. Patients who discontinue from study treatment (either for toxicity or physician choice) and have not progressed will continue to be followed for progression as per the protocol.

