10.4 DEFINITIONS OF TUMOR RESPONSE AND PROGRESSION

Responses will be categorized by the IRC as CR, PR, SD, or PD. In addition, a response category of not evaluable (NE) is provided for situations in which there is inadequate information to otherwise categorize response status.

UTX-IB-301

The best overall response will be determined. The best overall response is the best response recorded from the start of treatment until disease/recurrence progression (taking as a reference for disease progression the smallest measurements recorded since treatment started). Where imaging data are available, these data will supersede physical examination data in determining tumor status.

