11.10 STATISTICAL ANALYSES

11.10.1 PRIMARY EFFICACY VARIABLES

The ORR is defined as the proportion of patients with a best overall response of partial response (PR) or complete response (CR). Patients who do not have a tumor response assessment for any reason will be considered non-responders and will be included in the denominator when calculating the ORR. For the ITT analysis, for each treatment group, the number of patients achieving a response will be divided by the total of patients in the ITT population to yield the proportion responding.

UTX-IB-301

The primary efficacy variable (i.e. ORR) will be analyzed in the ITT population first and then will also be analyzed for the Treated Population.

The ORR will be compared between treatment groups by a Fisher's Exact Test. Testing of ORR will be at the 5%, 2-sided statistical significance level.

ORR will also be analyzed based on Per Protocol patients. Additional sensitivity analyses will also be performed as appropriate.

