11.10.2.1.6 PROGRESSION-FREE SURVIVAL

Progression-free survival is defined as the time from the date of randomization until the date of first documentation of definitive disease progression or date of death from any cause, whichever occurs first. Patients who die without a reported prior progression will be considered to have progressed on the day of their death. Patients who did not progress or are lost to follow-up will be censored at the day of their last tumor response assessment. If no baseline or post-baseline assessment is available, the patient will be censored at the date of randomization. If death or PD occurs after 2 or more consecutive missing tumor response assessments, censoring will occur at the date of the last response assessment prior to the missed assessments. The use of a new anticancer therapy prior to the occurrence of PD will result in censoring at the date of last tumor response assessment prior to initiation of new therapy.

This variable will be analyzed via Kaplan-Meier methodology. The median PFS will be estimated for each arm, however no formal hypothesis testing will be conducted.

UTX-IB-301

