6.1 PRIMARY EFFICACY OUTCOME

6.1.1 PRIMARY OBJECTIVE: OVERALL RESPONSE RATE

ORR is defined as the proportion of patients with a best overall response of partial response (PR) or complete response (CR). Patients who do not have a tumor response assessment for any reason will be considered non-responders and will be included in the denominator when calculating the ORR. For the ITT analysis, for each treatment group, the number of patients achieving a response will be divided by the total of patients in the ITT population to yield the proportion responding.

The primary efficacy variable (i.e. ORR) will be analyzed in the ITT population first and then will also be analyzed for the Treated Population.

The ORR will be compared between treatment groups by the CMH Test controlling for the randomization strata. Testing of ORR will be at the 5%, 2-sided statistical significance level.

ORR will also be analyzed based on Per Protocol patients. Additional sensitivity analyses will also be performed as appropriate.

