6.2 ANALYSIS METHODS: DOR AND PFS

The date of definitive progression will be the timepoint at which progression is first identified and confirmed by the independent radiographic committee. Death following the discontinuation of study drug will be considered as an event for the DOR and PFS calculation. Data will be censored on the date of the last tumor assessment (including assessments with a Not Evaluable (NE) outcome) for patients who:

- Start alternative anti-tumor therapy prior to disease progression
- Do not have disease progression within 30 days after discontinuation of study drug(s)

TG Therapeutics, Inc. UTX-IB-301 SAP

secondary outcomes will be tested:

If the primary efficacy analysis of ORR is statistically significant for the ITT population, the following

- Complete response rate
- Duration of response
- · Time to response

For each of these outcomes, ublituximab + ibrutinib will be compared to ibrutinib. The Hochberg approach will be used to control the type I error rate. The null hypotheses state that the secondary outcomes do not differ between ublituximab + ibrutinib and ibrutinib. The three p-values associated with these three secondary outcomes are denoted p_1 , p_2 , and p_3 . The ordered p-values, from largest to smallest, are denoted $p_{(1)} \ge p_{(2)} \ge p_{(3)}$. Specifically:

- If $p_{(1)}$ is less than 0.05, all three null hypotheses will be rejected.
- Otherwise, if $p_{(2)}$ is less than 0.025, the null hypotheses associated with $p_{(2)}$ and $p_{(3)}$ will be rejected.
- Otherwise, if $p_{(3)}$ is less than 0.0167, the null hypothesis associated with $p_{(3)}$ will be rejected.

If the primary efficacy analysis of ORR is not statistically significant, the secondary efficacy variable defined above will not be formally conducted.

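### The best-response window closes only at progression, so a PR or CR first seen after a switch to another CLL therapy can count in the primary ORR

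*Protocol*

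**What the plan says.** - **Response window.** Protocol 10.4: "The best overall response is the best response recorded from the start of treatment until disease/recurrence progression". New anticancer therapy is not mentioned.
- **Primary endpoint.** Protocol 11.10.1 and SAP 6.1.1 both define ORR as the share of patients whose best overall response is PR or CR. Patients with no response assessment count as non-responders. Neither section adds a rule for new therapy.
- **Other response endpoints.** CR rate (Protocol 11.10.2.1.1, SAP 6.1.2.1) also uses best overall response. Time to response (Protocol 11.10.2.1.3, SAP 6.1.2.3) runs to the first documented CR or PR. Neither has a cut at new therapy.
- **Assessments after study drug stops.** Protocol 6.4: "Patients who discontinue from study treatment (for reasons other than progressive disease) will continue to be followed for progression". Protocol 10 asks for response, not only progression, to be assessed: "If a patient is off study in follow up, assess for response every 3 months".
- **New therapy elsewhere.** For PFS, Protocol 11.10.2.1.6 says: "The use of a new anticancer therapy prior to the occurrence of PD will result in censoring". SAP 6.1.2.5 and its Table 3 repeat this. SAP 6.2, headed for DOR and PFS, lists among the patients to be censored those who "Start alternative anti-tumor therapy prior to disease progression".

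**The concern.** The primary objective is the effect of adding ublituximab to ibrutinib. A response first seen on a third agent does not measure that, yet the stated window does not exclude it.

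The plan recognises that new therapy breaks the link between study treatment and outcome, because it censors PFS and DOR there. It says nothing on this for the endpoint that carries the primary test.

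The SAP describes the trial as open label, so decisions to stop and switch are made knowing the arm. Blinded image review does not remove that. ORR also gates the formal tests of CR rate, DOR and time to response (the Hochberg procedure in the SAP), so a changed ORR verdict would carry through to them.

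**Working it through.** **Step 1. Can such a response be recorded before the ORR analysis?**

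- A patient may stop for toxicity, investigator discretion or other reasons without progression (Protocol 6.4) and stays in follow-up with response assessments every 3 months (Protocol 10).
- Enrolment is expected to take 18 to 24 months (Protocol 6.3). The ORR analysis waits until every ITT patient has had the opportunity for at least 16 weeks of evaluation (SAP 3.5.1).
- 16 weeks is 112 days, or about 3.7 months. The earliest patients could have about 18 + 3.7 = 21.7 to 24 + 3.7 = 27.7 months of follow-up; the last patient may have only 16 weeks.

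There is time for an early enrollee to stop, switch and respond, and little for a late one.

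**Step 2. Does any rule exclude it?**

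| Endpoint | Rule at new therapy |
|---|---|
| ORR | none (Protocol 10.4, 11.10.1; SAP 6.1.1) |
| CR rate | none (Protocol 11.10.2.1.1; SAP 6.1.2.1) |
| Time to response | none (Protocol 11.10.2.1.3; SAP 6.1.2.3) |
| PFS | censored (Protocol 11.10.2.1.6; SAP 6.1.2.5, Table 3, 6.2) |
| DOR | censored (SAP 6.2) |

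Protocol 10.3 refers to response during treatment, but there it names the baseline measurements used as reference. It does not close the window in 10.4.

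There is one side effect. If DOR is censored at the last assessment before new therapy, as PFS is, a patient whose first response follows the switch has a censoring date earlier than the response date.

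**Step 3. Scale.**

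No figure in the plan can be reproduced, because the public copy shows no assumed response rates. About 120 patients randomised 1:1 (SAP 3.6) gives about 60 per arm, so one reclassified patient is 1/60 = 1.7 points of that arm's ORR.

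The response counts below are assumptions. The SAP specifies a CMH test stratified by prior lines of therapy. Stratum sizes are not given, so I use the unstratified Mantel-Haenszel (MH) form. Fisher's exact test is shown beside it because Protocol 11.10.1 names that test.

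With a responders in Arm A, m responders in total, n = 60 per arm and N = 120:

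V = n·n·m·(N − m) / [N²(N − 1)], and χ² = (a − m/2)² / V on 1 df.

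- 54/60 v 46/60: m = 100, V = 60·60·100·20/(120²·119) = 4.202, χ² = 4²/4.202 = 3.81, p = 0.051.
- Add one post-switch response in Arm A (55/60 v 46/60): m = 101, V = 60·60·101·19/(120²·119) = 4.032, χ² = 4.5²/4.032 = 5.02, p = 0.025.

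| Arm A v Arm B with the cut | Post-switch responses added | MH p | Fisher p |
|---|---|---|---|
| 54/60 v 46/60 | 1 in A | 0.051 → 0.025 | 0.085 → 0.043 |
| 52/60 v 43/60 | 2 in B | 0.044 → 0.106 | 0.071 → 0.163 |
| 48/60 v 36/60 | 2 in B | 0.017 → 0.044 | 0.028 → 0.067 |
| 54/60 v 42/60 | 2 in B | 0.006 → 0.019 | 0.011 → 0.032 |
| 45/60 v 30/60 | 4 in B | 0.005 → 0.035 | 0.008 → 0.054 |
| 45/60 v 27/60 | 4 in B | 0.001 → 0.008 | 0.001 → 0.013 |

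Rows 1 and 2 were chosen close to 0.05; the others show how quickly the effect fades. In row 2 the verdict changes only under MH, because Fisher is already above 0.05. In rows 3 and 5 it changes only under Fisher.

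**The case against.** **The plan is silent; it does not say such scans count.** A reader might infer that responses to another drug will be credited to the study arm. The documents do not go that far. The review committee assigns the responses, its methods sit in a charter that is not among the documents (Protocol 10.2), and that charter could contain a cut. This limits the claim to what can count as written. It does not remove the point: the window of the primary endpoint belongs in the protocol and SAP, and neither refers to a cut held elsewhere.

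**Different endpoints may have different rules.** A reader might call the plan self-contradictory because PFS is censored at new therapy and ORR is not. That is too strong. Counting every response before progression can be a legitimate treatment-policy choice. However, no text declares that choice for ORR.

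**The group is narrow.** To matter, a patient must stop without progression, have no earlier PR or CR, start another therapy before progression, and then respond by blinded review before the analysis. An Arm A patient who stops only one drug may continue the other (Protocol 8.4.1). This stands, and it holds the size down.

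**Nothing shows that one arm would gain.** Open-label conduct makes unequal switching possible, but no figure in the documents supports a direction.

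**Conclusion.** The gap is real and should be closed. The stated window closes only at progression, off-treatment response assessments continue, and no rule excludes a response first seen after new therapy from ORR, CR rate or time to response.

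The size is 1.7 points of ORR per such response, assuming about 60 patients per arm. The number of switchers is not given and the direction is unknown. A reader might infer from the first row of the table that the trial's conclusion is fragile. The documents do not support that, because the counts are assumed and one or two responses change significance only when the result is near 0.05. At 54/60 v 42/60, two extra Arm B responses leave p at 0.019 (MH).

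Two extensions are also tempting and not established here. One is moving the start of the window to randomisation: nothing in this point turns on the start, and patients without a response assessment are already non-responders. The other is applying the cut to MRD negativity, which has its own inclusion rule in SAP 6.1.2.4. That rule already counts patients who leave before 6 months without an MRD assessment as non-responders.

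**What to change.** In Protocol 10.4 and SAP 6.1.1, define best overall response from assessments between the start of treatment and the earlier of progression or start of new anticancer therapy. State that patients with no response by then stay in the denominator as non-responders. Apply the same cut to CR rate and time to response, and check that the review charter agrees.

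Report ORR without the cut as a sensitivity analysis, so that any influence of later therapy is visible. If the sponsor does intend a treatment-policy ORR, the documents must say so, with the cut version reported beside it.

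The cost is a short wording change in each document. The date of new therapy is already needed for PFS censoring, so no new data are required. The downside is that ORR may fall slightly.

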10.5 COMPLETE RESPONSE

To satisfy criteria for a CR, all of the following criteria must be met:

- No evidence of new disease
- ALC in peripheral blood of <4 x 10⁹/L
- Regression of all target nodal masses to normal size ≤1.5 cm in the LD
- Normal spleen and liver size
- Regression to normal of all nodal non-target disease and disappearance of all detectable
- non-nodal, non-target disease
- Morphologically negative bone marrow defined as <30% of nucleated cells being lymphoid cells and no lymphoid nodules in a bone marrow sample that is normocellular for age
- Peripheral blood counts meeting all of the following criteria:
 - \circ ANC >1.5 x 10⁹/L without need for exogenous growth factors (e.g., G-CSF)
 - Platelet count \geq 100 x 10 9 /L without need for exogenous growth factors
 - o Hemoglobin ≥110 g/L (11.0 g/dL) without red blood cell transfusions or need for exogenous growth factors (e.g., erythropoietin)

Patients who fulfill all the criteria for a CR (including bone marrow criteria) but who have a persistent anemia, thrombocytopenia, or neutropenia or a hypocellular bone marrow that is related to prior or ongoing drug toxicity (and not to CLL) will be considered as a CR with incomplete marrow recovery (CRi).

10.6 PARTIAL RESPONSE

To satisfy criteria for a PR, all of the following criteria must be met:

- No evidence of new disease
- A change in disease status meeting ≥2 of the following criteria, with 2 exceptions in which only 1 criterion is needed: 1) only lymphadenopathy is present at baseline; 2) only lymphadenopathy and lymphocytosis are present at baseline. In these 2 cases, only lymphadenopathy must improve to the extent specified below:
 - o In a patient with baseline lymphocytosis (ALC ≥4 x 10^9 /L), a decrease in peripheral blood ALC by ≥50% from baseline or a decrease to <4 x 10^9 /L
 - \circ A decrease by ≥50% from the baseline in the SPD of the target nodal lesions
 - o In a patient with enlargement of the spleen at baseline, a splenomegaly response as defined in Section 10.3.2
 - o In a patient with enlargement of the liver at baseline, a hepatomegaly response as defined in Section 10.3.2
 - A decrease by ≥50% from baseline in the CLL marrow infiltrate or in B-lymphoid nodules
- No target, splenic, liver, or non-target disease with worsening that meets the criteria for definitive PD

UTX-IB-301

- Peripheral blood counts meeting 1 of the following criteria:
 - o ANC >1.5 x 10^9 /L or >50% increase over baseline without need for exogenous growth factors (e.g., G-CSF)
 - o Platelet count >100 x 10⁹/L or ≥50% increase over baseline without need for exogenous growth factors
 - o Hemoglobin >110 g/L (11.0 g/dL) or ≥50% increase over baseline without red blood cell transfusions or need for exogenous growth factors (e.g., erythropoietin)

10.7 STABLE DISEASE

To satisfy criteria for SD, the following criteria must be met:

- No evidence of new disease
- There is neither sufficient evidence of tumor shrinkage to qualify for PR nor sufficient evidence of tumor growth to qualify for definitive PD

10.8 DEFINITIVE DISEASE PROGRESSION

The occurrence of any of the following events indicates definitive PD:

- Evidence of any new disease:
 - o A new node that measures >1.5 cm in the LD and >1.0 cm in the LPD
 - o New or recurrent splenomegaly, with a minimum LVD of 14 cm
 - o New or recurrent hepatomegaly, with a minimum LVD of 20 cm
 - o Unequivocal reappearance of an extra-nodal lesion that had resolved
 - o A new unequivocal extra-nodal lesion of any size
 - *New non-target disease (e.g., effusions, ascites, or other organ abnormalities related to CLL)

*Isolated new effusions, ascites, or other organ abnormalities are not sufficient evidence alone of PD unless histologically confirmed. Thus, a declaration of PD should not be made if this is the only manifestation of apparently new disease.

- Evidence of worsening of target lesions, spleen or liver, or non-target disease:
 - o Increase from the nadir by ≥50% from the nadir in the SPD of target lesions
 - Increase from the nadir by \geq 50% in the LD of an individual node or extra-nodal mass that now has an LD of >1.5 cm and an LPD of > 1.0 cm
 - Splenic progression, defined as an increase in splenic enlargement by ≥50% from nadir (with a minimum 2 cm increase and a minimum LVD of 14 cm)
 - Hepatic progression, defined as an increase in hepatic enlargement by ≥50% from nadir (with a minimum 2 cm increase and minimum LVD of 20 cm)
 - Unequivocal increase in the size of non-target disease (e.g., effusions, ascites, or other organ abnormalities related to CLL)
 - Transformation to a more aggressive histology (e.g., Richter's syndrome) as established by biopsy (with the date of the biopsy being considered the date of CLL progression if the patient has no earlier objective documentation of CLL progression).
- Decrease in platelet count or hemoglobin that is attributable to CLL, is not attributable to an autoimmune phenomenon, and is confirmed by bone marrow biopsy showing an infiltrate of clonal CLL cells

UTX-IB-301

- \circ The current platelet count is <100 x 10 9 /L and there has been a decrease by >50% from the highest on-study platelet count
- O The current hemoglobin is <110 g/L (11.0 g/dL) and there has been a decrease by >20 g/L (2 g/dL) from the highest on-study hemoglobin

If there is uncertainty regarding whether there is true progression, the patient should continue study treatment and remain under close observation pending confirmation of progression status by the IRC. In particular, worsening of constitutional symptoms in the absence of objective evidence of worsening CLL will not be considered definitive disease progression; in such patients, both CLL-related and non-CLL-related causes for the constitutional symptoms should be considered.

Worsening of disease during temporary interruption of study treatment (e.g., for intercurrent illness) is not necessarily indicative of resistance to study treatment. In these instances, CT/MRI or other relevant evaluations should be considered in order to document whether definitive disease progression has occurred. If subsequent evaluations suggest that the patient has experienced persistent definitive CLL progression, then the date of progression should be the time point at which progression was first objectively documented.

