10.3 IDENTIFICATION AND MEASUREMENT OF TUMOR LESIONS AND ORGANOMEGALY

10.3.1 TARGET LESIONS

At baseline, up to 6 lymph nodes should be selected as target lesions that will be used to quantitate the status of the disease during study treatment. Ideally, the target lesions should be located in disparate regions of the body. Only peripheral nodes need be selected as target lesions. However, it is optimal if mediastinal and retroperitoneal areas of disease are assessed whenever these sites are involved.

Target lesions will be measured and recorded at baseline and as per the study assessment schedule. The cross-sectional dimensions (the largest cross-sectional diameter, i.e., the LD \times LPD) will be recorded (in cm) for each target lesion. The product of the perpendicular diameters (PPD) (in cm²) for each target lesion and the sum of the products (SPD) (in cm²) for all target lesions will be calculated and recorded. The baseline SPD will be used as references by which objective tumor response will be characterized during treatment. The nadir LD of individual lesions and the nadir SPD will be used as references by which CLL progression will be characterized. All LD and LPD diameters will be reported in centimeters and all PPDs and SPDs will be reported in centimeters squared.

A nodal mass may be selected as a measurable nodal target lesion if it is > 1.5 cm in long axis diameter and > 1.0 cm in short axis diameter.

A new node that measures >1.5 cm in the LD and >1.0 cm in the LPD will be considered progressive disease.

In cases in which a large lymph node mass has split into multiple components, all subcomponents regardless of size will be used in calculating the SPD. Progression of the lesion will be based on the SPD of sub-components. Lesion sub-components will have the true PPDs calculated. Similarly, lesion sub-components that are visible but neither abnormal nor measurable will have the default PPD of $1.0~\rm cm^2$ ($1.0~\rm cm \times 1.0~\rm cm$) used in calculating the SPD.

If lesions merge, a boundary between the lesions will be established so the LD of each individual lesion can continue to be measured. If the lesions have merged in a way that they can no longer be separated by this boundary, the newly merged lesion will be measured bi-dimensionally.

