10.3.3 NON-TARGET LESIONS

Any other measurable and abnormal nodal lesions not selected for quantitation as target lesions may be considered non-target lesions. In addition, non-measurable evidence of CLL such as nodal lesions with both diameters <1.0 cm, extra-nodal lesions, bone lesions, leptomeningeal disease, ascites, pleural or pericardial effusions, lymphangitis of the skin or lung, abdominal masses that are not confirmed and followed by imaging techniques, cystic lesions, previously irradiated lesions, and lesions with artifacts may be considered as non-target disease.

The presence or absence of non-target disease should be recorded at baseline and at the stipulated intervals during treatment. If present at baseline, up to 6 non-target lesions should be recorded. The non-target disease at baseline will be used as a general reference to further characterize regression or progression of CLL during assessments of the objective tumor response during treatment. Measurements are not required and these lesions should be followed as "present" or "absent".

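### The SPD limb of definitive progression has no node-size condition, so a patient with few, small target nodes can be scored PD while every node still meets the CR nodal criterion

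*Protocol*

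**What the plan says.** Protocol 10.8 opens its list with "The occurrence of any of the following events indicates definitive PD", so each limb is sufficient alone. The nodal sum limb reads "Increase from the nadir by ≥50% from the nadir in the SPD of target lesions" and stops there. The measured limbs around it go further:

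- an individual node must be one "that now has an LD of >1.5 cm and an LPD of > 1.0 cm";
- a new node counts as "A new node that measures >1.5 cm in the LD and >1.0 cm in the LPD";
- splenic progression is qualified "with a minimum 2 cm increase and a minimum LVD of 14 cm", and the hepatic limb is built the same way, with 20 cm.

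Protocol 10.3.1 sets the reference: "The nadir LD of individual lesions and the nadir SPD will be used as references by which CLL progression will be characterized". It puts no floor under the nadir SPD. Its one default value, 1.0 cm² per product, is for small sub-components of a split nodal mass.

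On the response side, 10.5 asks for "Regression of all target nodal masses to normal size ≤1.5 cm in the LD", and 10.3.3 lists as "non-measurable evidence of CLL such as nodal lesions with both diameters <1.0 cm".

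Appendix A reproduces the published criteria that Protocol 4.1 and section 10 cite. Its PD list has no SPD limb; for nodes that are already known it requires a 50% rise in the greatest diameter. Under PR it disregards growth below 25% in nodes under 2 cm.

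**The concern.** In a patient whose nodes have regressed well, the nadir SPD is small, so a 50% rise over it is a small absolute change. One scan can then satisfy the nodal part of CR and the definition of PD. The text does not say which prevails: PR (10.6) and SD (10.7) exclude worsening that reaches PD, whereas CR (10.5) excludes only new disease.

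IRC findings are primary for PFS and the other tumor-control endpoints (Protocol 10 and 10.2). DOR belongs to the Hochberg family in the SAP's multiplicity rule. Best overall response is read only up to progression (Protocol 10.4), so a CR reached after such a call would not count. PD is also a listed reason for stopping study treatment (Protocol 6.4).

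**Working it through.** The plan gives no figure to reproduce here. The check is geometry from the written rules, then a simulation under a stated assumption.

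**Inputs from the Protocol.** PD on SPD at 1.5 times nadir or more (10.8); normal target node at LD ≤1.5 cm (10.5); individual-node size condition LD >1.5 cm and LPD >1.0 cm (10.8); up to six target nodes (10.3.1); entry possible with one measurable node (5.1, criterion 4).

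**1. Growth needed.** SPD is the sum of LD x LPD. If all diameters grow by a factor k, SPD grows by k². PD needs k² ≥ 1.5, so k ≥ √1.5 = 1.2247, or 22.5% per diameter.

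**2. Nadirs at risk.** Nodes stay normal under 10.5 if 1.2247 x nadir LD ≤ 1.5 cm, so nadir LD ≤ 1.5 / 1.2247 = 1.22 cm.

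**3. Examples.**
- Two nodes of 0.8 x 0.6 cm: SPD 2 x 0.48 = 0.96 cm². Both become 1.0 x 0.75 cm: SPD 2 x 0.75 = 1.50 cm². The ratio is 1.50 / 0.96 = 1.56, a 56% rise, so PD.
- One node of 1.0 x 1.0 cm reaches 1.50 cm² at 1.225 x 1.225 cm (2.2 mm each way).
- One node of 1.2 x 0.8 cm: 0.96 to 1.44 cm² at 1.47 x 0.98 cm (2.7 and 1.8 mm).

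Every node is still ≤1.5 cm in LD. None meets the individual-node limb, which needs 50% growth in LD and a size these nodes do not have.

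**4. Where it does not bite.** If only LD grows, a 1.0 cm node must reach 1.5 cm. If one of six 1.0 x 1.0 cm nodes grows alone, SPD must go from 6 to 9 cm², so that node's product must be 9 - 5 = 4 cm², about 2.0 x 2.0 cm. That node is no longer normal.

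**5. Against Appendix A.** Growth of 22.5% is below its 50% diameter rule for PD. It is also below its 25% small-node tolerance, if that is read as a diameter.

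**6. False PD in stable nodes.** True sizes are held constant over six scans, with independent normal error on each diameter. PD is called when SPD is at least 1.5 times the lowest earlier SPD. There were 100,000 simulated patients per cell. The error SD is an assumption; the documents give none.

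| Assumed SD | Target nodes | 1.0 x 0.8 cm | 0.8 x 0.6 cm |
|---|---|---|---|
| 0.5 mm | 1 | 0.3% | 4% |
| 0.5 mm | 2, 3 or 6 | 0% | 0.1% or less |
| 1 mm | 1 | 32% | 57% |
| 1 mm | 2 | 7% | 25% |
| 1 mm | 3 | 1.4% | 10% |
| 1 mm | 6 | 0.01% | 0.6% |
| 1.5 mm | 1 | 68% | 83% |
| 1.5 mm | 2 | 38% | 62% |
| 1.5 mm | 3 | 20% | 45% |
| 1.5 mm | 6 | 2% | 14% |

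With three scans instead of six, SD 1 mm and 1.0 x 0.8 cm nodes, the rates are 10% (one node) and 1.7% (two).

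**7. With the individual-node size condition added to the SPD limb.** False PD is at most 0.03% in every cell above. It does not vanish near the threshold: for a single stable 1.4 x 1.0 cm node, also normal under 10.5, about 6% remains at SD 1 mm and roughly a quarter at SD 1.5 mm.

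**The case against.** The best defence is that progression is called by a blinded IRC under a charter that is not among the documents and may contain a floor. Uncertain progression is referred to that committee (10.8), and SAP 6.2 dates progression when the committee identifies and confirms it. This limits what can be said about how often false calls would occur in practice. It does not change the written rule: a computed 56% rise is not uncertain under 10.8, no size threshold is given to the IRC in either document, and no repeat scan is required.

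Several stronger readings are tempting and are not supported.

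- *The SPD limb alone lacks a floor.* It does not: new extra-nodal lesions and growth of non-target disease have no numeric floor either. The contrast holds for the measured limbs only.
- *A 2 mm change makes PD.* Only if both diameters grow, in the sole target node or in all of them together. With six nodes the risk is small unless reader error is large.
- *The better arm is penalised.* The documents give no figure for how many patients per arm reach such small nadirs. The combination effect described in Protocol 3.4 beyond response rates is on lymphocytosis, not node size.
- *The primary endpoint is at risk.* ORR uses best response, and a patient regressing from a node of at least 2.0 cm to these sizes will usually have met the SPD part of PR already.

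The stakes are further limited. The Protocol plans no formal PFS test, the SAP says PFS may not be formally analysed at the ORR analysis, and DOR is tested only if ORR is significant. Six scans with nodes already regressed at the first would run to Cycle 15.

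**Conclusion.** The concern stands in a bounded form. As written, 10.8 can classify as definitive PD a scan on which every target node is normal under 10.5, and Appendix A would not call the same nodal growth PD. This follows from the text and needs no assumption. It applies to patients with one or a few target nodes, all with LD up to about 1.22 cm at nadir.

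The frequency is not known. It rests on the assumed reader error, the number of target nodes, their size at nadir and the number of later scans. For the two node sizes simulated, it runs from essentially zero (SD 0.5 mm, two or more nodes) to 83% (SD 1.5 mm, one 0.8 x 0.6 cm node). PFS, DOR and possibly later CR are affected, with little effect on ORR. The direction of any effect between arms is not established. The point deserves correction because an endpoint definition contradicts itself, not because bias of a given size has been shown.

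**What to change.** 1. Reconcile 10.5, 10.8, Appendix A and the IRC charter so that one scan cannot meet both the nodal CR criterion and PD. If the charter already has a floor, state it in the Protocol and in SAP 6.2.
2. In SAP 6.2, for IRC-derived PFS and DOR, count an SPD-only increase as progression only if at least one target node also has LD >1.5 cm and LPD >1.0 cm, the condition 10.8 already applies to an individual node.
3. Fix this before database lock and have the blinded IRC apply it identically to both arms. Report the derivation as currently written as a sensitivity analysis. The trial is open label and data may already exist, so progressions already scored should not be revised outside such a prespecified rule.
4. How the reconciled definition bears on stopping treatment is for the sponsor to settle; nothing is proposed on that here.

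The cost is a short text change in the Protocol, SAP and charter, a blinded review of the SPD-only progressions, and one extra analysis. There are two downsides: true regrowth spread across still-normal nodes may be dated one scan later, and false PD is reduced but not removed for nodes near 1.5 x 1.0 cm.
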